- Any condition that, in the opinion of the investigator, would interfere with the study conduct or the safety of the participant

Additional Exclusion Criteria: Outpatient Arm (in addition to general exclusion criteria above)

- Decrease in FEV1 > 10% from baseline over last 12 months
- Antibiotic Initiation for acute CF exacerbation
- Hospitalization for CF Exacerbation

Additional Exclusion Criteria: Inpatient Arm (in addition to general exclusion criteria above)

- Failure to increase FEV1 $\geq 10\%$ from initial PFTs on admission by day 9 of hospitalization.

Our patients will be recruited from our CF outpatient Clinic and from our CF inpatient population. Participants will be randomly assigned to perform airway clearance with the Standard Airway Clearance device (SACD) or Portable Internal Airway Percussion device (PIAPD). A large majority of our patients will be using VEST therapy as their standard of care airway clearance. A few might be using an Intrapulmonary Percussion Device that uses a mechanism different from the device we will be testing. Based on past experience, it is unlikely that this will present a significant source of variability.

After discussing the study with a prospective participant and obtaining informed consent, participants will be randomized to either the standard of care or experimental group:

Outpatient arm:

On day 1, baseline FEV1 as measured on Smart One® portable home spirometer (Figure 1) and pulse oximetry will be obtained before and 2 hours after airway clearance, either performed with SACD method, PIAPD at 15hz. The frequency of the device will stay at 15 hz for the duration of the study as it has been previously shown to be the most effective frequency for better airway clearance (i.e., getting deeper into the airways). Participants will also be asked to give a rating of breathing effort using a Modified Borg Dyspnea Scale.

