For the next two weeks, airway clearance therapy, either performed with SACD method or PIAPD, will be performed by the patient daily (CF patients perform airway clearance daily as part of standard of care for their disease). Spirometry/pulmonary function testing will be collected twice per week over the two-week period with a pre and post FEV1, pulse oximetry, and rating of breathing effort. This testing will be done via telemedicine so that the PI or co-investigator can assist the patient with the PIAPD if necessary and conduct the testing in a safe and efficacious manner. At the end of the two weeks, the participant will be asked to complete a short survey regarding the ease of use and acceptability of the airway clearance device they had been using for the first part of the study.

At the end of the initial 2-week period, the patient will be crossed-over to the other arm of the study and the same procedures will be repeated as per the above procedures. At the end of the study, patients will return the PIAPD device to the study team.

FIGURE 1

Figure 1: Smart One® portable home spirometer is the standard of care for at-home measurement of FEV-1.

Inpatient arm:

Patients who are admitted to the hospital for a normal seasonal disturbance of their CF are admitted, as SOC, for a 14-day in-patient stay. When patients are admitted, they bring their VEST system, as this is the standard of care device used by over 95% of CF patients for airway clearance therapy. Following admission, patients will be informed of the study by the PI or one of the designated co-investigators. All study procedures will be explained and ample time to ask questions will be allotted. If the patient agrees to participate written informed consent will be obtained and the following procedures performed:

Hospital Stay Days 1-3: Patients will only use their SOC airway clearance therapy. This will allow for a “wash-out period” providing all the patients with good airway clearance prior to collecting data (some patients may have had poor compliance prior to hospitalization). The participant will also be asked to complete a short survey regarding the ease of use and acceptability of their SOC airway clearance device, at the end of this 3-day wash-out period. Furthermore, during this period, we will get daily spirometry with a portable spirometer once per day after first airway clearance of the day, along with pulse oximetry.

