Hospital Stay Day 4: If, in the judgement of the PI, the participant has stabilized, we will randomize them to use either their SOC device or the study device. On Day 4, patients will be randomized to SOC or the new airway clearance device. We will collect the patient’s ratings of breathlessness with the Modified Borg Dyspnea Scale and perform spirometry again with the Smart One® portable spirometry device before and two hours after airway clearance procedures for the first airway clearance of the day. We will also obtain pulse oximetry.

Hospital Stay Day 5: we will alternate the modality for the first airway clearance session of the day (using whichever device they were not randomized to use on Day 4), repeating the Modified Borg Dyspnea Scale and performing spirometry again before and two hours after airway clearance along with pulse oximetry. At this point, they will have used both the airway clearance devices, and they will be asked to complete a short survey regarding the ease of use and acceptability of the study airway clearance device.

Hospital Stay Days 6-9: we will continue with daily spirometry, dyspnea measurements and pulse oximetry once per day after the first airway clearance of the day using the study device.

Hospital Stay Days 10-14: patients who have increased their FEV1 by at least 10% from admission by day 9 of hospitalization and whose symptoms have clinically improved, will be given the choice of whether to use their SOC device or the experimental study device. Whichever device they choose, they will use for two airway clearance sessions, along with dyspnea measurements, and pulse oximetry on days 10-14 of hospitalization.

At the end of the two weeks, the participant will be asked to complete a short survey regarding the ease of use and acceptability of each airway clearance device they had been using for the study. At the end of the study, we will ask that the patient return the experimental device to the study team.

FIGURE 2

Figure 2: The Vest® Airway Clearance System is the standard of care for airway clearance in both adult and pediatric

Safety Endpoints:

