We shall cross-tabulate the pre- and post-treatment spirometry measures for study condition and group. Significance for association will be obtained by repeated measures ANOVA. The false positive and false negative rates will be estimated by exact binomial confidence limits. This is a pilot study that is seeking a promising outcome as opposed to a definitive one. We shall consider the result as promising if (a) no false positives occur and (b) the false negative rate is below 50%.

Power/Sample Size: The study will have a goal to recruit 50 CF (10 inpatient and 40 outpatient) patients. Initial data analysis to be completed after the first 25 patients have completed each test condition.

Measurable outcomes and expected timeline: We expect the PIAPD is equal to standard airway clearance in CF patients. We expect PIAPD will decrease the sense of breathing effort and increase patient sense of efficacy.

Compliance/Accountability/Regulatory

Statement of Compliance

This study will be conducted in compliance with the protocol and will be generally consistent with current Good Clinical Practices (GCP), adopting the principles of the Declaration of Helsinki and all applicable regulatory requirements (ICH E6, 45CFR46, and FDA 21CFR sections 11, 50, 56, 312).

Prior to study initiation, the protocol and the informed consent documents will be reviewed and approved by UF's Institutional Review Board (IRB). Any amendments to the protocol or consent materials will be approved before they are implemented.

Adverse Event Reporting and Safety Monitoring

In the event of an adverse event the following definitions and processes will be used/followed:

Adverse Event Definitions

In this clinical research study, an adverse event (AE) is any occurrence or worsening of an undesirable or unintended sign, symptom or disease that is associated with study procedures. As an observational study, AEs occurring between study visits will not be reported unless deemed associated with study procedures. Throughout the study, the investigator must record AEs related to study procedures on source documents regardless of severity.

Unexpected Adverse Event

An AE is considered unexpected when the nature (specificity) or severity of the event is not consistent with the risks described in the protocol or informed consent document for specific protocol-required interventions.

Grading Adverse Event Severity

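### Repeated measures ANOVA is named without a rule for combining sessions, pooling arms or handling missed readings; a mixed model on all available tests suits the unequal schedule better

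*Combined protocol and SAP*

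**What the plan says.** The Statistical Analysis section describes the data as follows: "We shall cross-tabulate the pre- and post-treatment spirometry measures for study condition and group". The test follows: "Significance for association will be obtained by repeated measures ANOVA". The factors of the ANOVA, the handling of multiple sessions, the pooling of the two arms and the treatment of missing readings are not stated. The word group is not defined there. It could mean inpatient/outpatient or the randomised assignment.

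The schedule differs by arm.

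- **Outpatient arm.** FEV1 is taken before and 2 hours after clearance on day 1. Over the next two weeks it is "collected twice per week over the two-week period with a pre and post FEV1". Then "the patient will be crossed-over to the other arm of the study and the same procedures will be repeated".
- **Inpatient arm.** On Hospital Stay Day 4, spirometry is done "before and two hours after airway clearance procedures for the first airway clearance of the day". On Day 5, "we will alternate the modality for the first airway clearance session of the day", again with spirometry before and two hours after. Days 1-3 and 6-9 have only a single reading after clearance each day, and the text for Days 10-14 names no spirometry.

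Power/Sample Size sets a target of 50 patients, 10 inpatient and 40 outpatient. Safety Endpoints lists reasons for ceasing the study device. They include a fall in FEV1 of more than 10%, severe breathlessness and, for outpatients, simply not wanting to continue with it.

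**The concern.** Classical repeated measures ANOVA works on one common, complete set of within-patient cells. This schedule gives the two arms very different numbers of pre/post readings, and the plan does not say how to reduce them to a common set. The analyst must choose, and the choice decides who is analysed.

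With sessions kept separate, an outpatient who misses one reading out of many leaves the analysis, and the inpatients cannot be included beside the outpatients. With sessions averaged, those two problems go away. However, the average hides how many tests lie behind each value, and a patient with nothing on one device still goes. Some of those patients will have stopped for reasons listed under Safety Endpoints, which are linked to the device and to FEV1 itself. In a crossover of 50 patients meant to inform a non-inferiority question, these choices should be fixed before the data are seen.

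**Working it through.** **Plan's own figure.** 10 + 40 = 50, which adds up. The documents state no count of readings, so the counts below come from the schedule. A test here means one session with a pre and a post reading.

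**Readings per patient**

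- Outpatient: (1 day-1 test + 2 per week x 2 weeks) = 5 tests per device; 5 x 2 readings x 2 devices = 20.
- Outpatient, if day 1 is one of the twice-weekly tests: 4 x 2 x 2 = 16. The text places the twice-weekly tests in the two weeks after day 1, which favours 20.
- Inpatient: 1 test per device x 2 readings x 2 devices = 4. The 3 + 4 = 7 single readings on Days 1-3 and 6-9 are not pre/post pairs.
- Whole study: 40 x 20 + 10 x 4 = 840.

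**Behaviour of the method.** On simulated data with this layout and factors device, session and pre/post:

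- A standard repeated measures ANOVA routine rejected both arms together as unbalanced.
- It ran on complete outpatients alone, then failed when one reading was removed.
- After averaging to device by pre/post (4 cells per patient), both arms fitted one ANOVA, with or without that reading.
- A mixed model kept all 50 patients and 839 of 840 readings.

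**Outpatients retained, sessions kept separate.** Share complete = (1 - m)^k, with m an assumed independent miss rate. SE factor = 1/sqrt(share), relative to all 40.

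| Unit missed | m | k | Share | Of 40 | SE factor |
|---|---|---|---|---|---|
| Whole test | 5% | 10 | 0.599 | 24 | 1.29 |
| Whole test | 10% | 10 | 0.349 | 14 | 1.69 |
| Single reading | 2% | 20 | 0.668 | 27 | 1.22 |
| Single reading | 5% | 20 | 0.358 | 14 | 1.67 |
| Single reading | 10% | 20 | 0.122 | 5 | 2.87 |

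Whole-test misses are the more realistic case for scheduled appointments, because pre and post readings would tend to be missed together. With 16 readings (8 tests), 0.95^8 = 0.663 and 0.90^8 = 0.430 leave about 27 and 17 of 40.

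**Outpatients retained, sessions averaged.** A patient is lost only if all five tests on a device are missed. At 10% the chance is about 2 x 0.1^5 = 0.00002, so essentially all 40 remain. This covers sporadic misses only. A patient who leaves before using one of the devices is lost whatever the miss rate.

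**Weighting after averaging.** Let s² be the test-to-test variance of the pre-to-post change and t² the patient-by-device variance. The variance of one patient's device difference is 2(t² + s²/5) for an outpatient and 2(t² + s²) for an inpatient. The ratio runs from 1 (s² = 0) to 5 (t² = 0). At the extreme of 5, write v for the outpatient variance:

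- Equal weights: (40v + 10 x 5v)/50² = 0.036v.
- Inverse-variance weights: v/(40 + 10/5) = v/42 = 0.0238v.
- SE ratio: sqrt(0.036 x 42) = 1.23.

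Equal weighting therefore costs between nothing and 23% in SE. The documents give neither variance.

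**The case against.** The strongest reply is that the plan never names session as a factor. It speaks of pre and post measures by condition and group, and Specific Aims compares the change from before to 2 hours after between devices. Read that way, every patient has four cells, both arms fit one ANOVA, and a single missed reading costs nothing. This stands. A reader might infer that the arms cannot share an ANOVA, or that one missed reading necessarily removes an outpatient. The documents do not support either as a flat statement; both depend on an unstated choice. Nor is it stated that the arms are to be pooled, so separate analyses are possible. In that case the outpatient problem remains only if sessions are kept separate.

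A reader might also infer that misses will be frequent because testing is at home in patients from age 6. The twice-weekly outpatient tests are conducted by telemedicine with an investigator assisting, which may keep misses low. The documents give no rate, so a collapse to 5 of 40 is only the far end of an assumed range.

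A mixed model is not free of assumptions either. It relies on data being missing at random, and the stopping rules make some missingness depend on device and outcome. This also stands and shapes the fix.

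Finally, the study is a pilot whose criterion for a promising result is not the ANOVA p-value. That limits the severity, but the ANOVA is still the only device comparison the plan names.

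**Conclusion.** The point holds in conditional form. The plan names a method that does not suit an unequal schedule as it stands, and it omits the rules that would make it fit. If sessions are kept separate, both arms cannot enter together, and about 24 or 14 of 40 outpatients are complete at assumed whole-test miss rates of 5% or 10%. If sessions are averaged, essentially all 40 survive sporadic misses. Unequal precision is then ignored, at a cost of up to 23% in SE in the pooled comparison, and patients with no data on one device are still excluded. These can include patients who stop under Safety Endpoints before using the study device or before crossing over.

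The retention figures rest on assumed, independent miss rates. The weighting figure assumes independent test errors and a common device effect. A reader might infer that complete-case exclusion would bias the result towards no difference. That is plausible if those who do badly on the device are the ones lost, but nothing in the documents fixes its direction or size. Because this is a pilot, the change is advisable rather than critical.

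**What to change.** In Statistical Analysis, replace repeated measures ANOVA with a linear mixed model fitted by REML to all available pre/post tests, for example on the change in FEV1 from before to 2 hours after clearance. Use fixed effects for device, period and arm (inpatient/outpatient), and random effects for patient and patient-by-device. For inpatients, Days 4 and 5 are the two periods. With one test per device, inpatients cannot separate the patient-by-device variance from test-to-test error, so that variance will be estimated essentially from outpatients; the plan should say so. When the change is the outcome, a missed reading removes that test and not the patient.

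Report the number of tests contributed per device and arm, and the reasons for missing tests. Because the model assumes data are missing at random, add a simple sensitivity analysis for patients who stop the study device under Safety Endpoints. One option is to fill in their unobserved study-device changes with values progressively worse than the model predicts.

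If the investigators prefer ANOVA, the plan should at least state the averaging rule, whether the arms are pooled and how patients with data on only one device are treated.

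The cost is a few sentences in the plan and a slightly more complex model in standard software. Visits, measurements and care do not change.

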Project Title: Airway Clearance for Pediatric and Adult Cystic Fibrosis Patients Using a Portable Intra-Pulmonary Percussion Device

Investigator(s): [name], [name], [name], [name], [name].

Abstract:

Airway clearance has a crucial role in the prevention of progression of lung disease in cystic fibrosis patients. Despite multiple options available for airway clearance, frequently cystic fibrosis patients have difficulties performing regular airway clearance in an at-home environment. We will compare pulmonary function testing and patient satisfaction with their current home device compared to the portable internal airway percussion device proposed (PIAPD). Our hypothesis is that there is no difference in pulmonary function testing after using PIAPD comparing to their home device. Our goal is to provide an equally effective, less expensive, alternative airway clearance technique for cystic fibrosis patients.

Background:

Cystic Fibrosis (CF) is an autosomal recessive disease that affects more than 30,000 people in the United States and more than 70,000 worldwide. The abnormal Cystic Fibrosis Transmembrane conductance regulator (CFTR) function leads to multiple organ manifestations. In the lungs, the dysfunctional CFTR mutation leads to abnormal thick, sticky mucus in the airways that traps microorganisms, leading to infections, inflammation and respiratory failure, which are the main causes of death in CF patients. Daily airway clearance plays a key role in preventing lung function deterioration in CF. Typically, a CF patient gets airway clearance therapy at least two times daily, each session lasting for about 30 minutes. There are different types of airway clearance therapies. Some of them are active, requiring patient cooperation and some coordination of breathing, while others are predominantly passive. In the United States, the most commonly utilized technique is high frequency chest wall oscillation, more commonly known as “the VEST”. This vibration loosens secretions in the bronchi that the patient will have to actively expel. The apparatus of vest therapy involves a wearable jacket, a hose pipe and an air compressor. This apparatus requires electric supply from the mains and is not portable.

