The PIAP device,(as pictured in Figure 4) that we have developed has been previously tested in several IRB-02 approved pilot studies here at the University of Florida by [name] in a population of healthy volunteers. Published results of these studies report this device's waves produce vibrations within the airways, loosening Airway Surface Liquid (ASL), enhancing airway clearance and decreasing the sense of breathing effort. Furthermore, the IAP device was found to painlessly increase exhalation of intra airway molecules and droplets in healthy individuals.

For this study, we would like to test this unique, custom designed, inexpensive, portable IAP device (PIAPD) as a comfortable alternative for airway clearance in CF patients.

Specific Aims:

1. To determine if Portable Internal Airway Percussion Device (PIAPD) is a non-inferior at-home method of airway clearance in patients with CF, we will compare changes in pulse oximetry and forced expiratory volume in one second (FEV1) prior to and 2 hours after airway clearance performed with standard airway clearance devices vs. the PIAPD. The primary endpoint will be a comparison of results of the aforementioned pulmonary function testing between the two devices.
2. Secondary endpoints include will include comparison of patient satisfaction (tolerability and acceptability) with standard airway clearance devices and PIAPD.
3. We will measure CF patient perception of breathing effort and device use for both methods.

Study Design: This is a pilot study where we aim to compare initial use of the standard airway clearance device (SACD) (as pictured in Figure 2) with subsequent use of a PIAPD in patients ages 6-21 years with stable CF. Our primary hypothesis, stated as Null, is that there is no effect of on FEV1 2 hours after use and there is no effect on perception of effort and efficacy for the PIAPD device.

General Inclusion Criteria:

- Ages 6-21 years
- Stable CF as determined by pulmonary physician assessment
- Assents to forego additional experimental treatments during the study
- Currently using and familiar with airway clearance therapy for treatment of CF
- Participant (or parent or legal guardian if the participant is a minor) is willing to provide Informed Consent

General Exclusion Criteria:

- FEV1 < 40% predictive
- Pneumothorax
- Hemoptysis

- COVID-19 diagnosis within last 14 days
- Non-compliance
- Inability to obtain informed consent

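### The plan's only success rule cannot be evaluated, because false positive and false negative are undefined, and it would not answer the non-inferiority aim even if they were defined

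*Combined protocol and SAP*

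**What the plan says.** The Abstract gives the hypothesis: "Our hypothesis is that there is no difference in pulmonary function testing after using PIAPD comparing to their home device". Specific Aims, aim 1, asks whether the PIAPD "is a non-inferior at-home method of airway clearance in patients with CF", and says how: "we will compare changes in pulse oximetry and forced expiratory volume in one second (FEV1) prior to and 2 hours after airway clearance", with the standard device against the PIAPD. The primary endpoint is the comparison of those results between the two devices.

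The Statistical Analysis section begins with a cross-tabulation of spirometry before and after treatment, by study condition and group. It continues: "Significance for association will be obtained by repeated measures ANOVA". Then: "The false positive and false negative rates will be estimated by exact binomial confidence limits". The study is described as a pilot that looks for a promising rather than a definitive outcome, and the rule follows: "We shall consider the result as promising if (a) no false positives occur and (b) the false negative rate is below 50" per cent.

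Power/Sample Size sets a goal of 50 patients (40 outpatient, 10 inpatient) and adds: "Initial data analysis to be completed after the first 25 patients have completed each test condition". It does not say whether the rule is applied at that point.

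**The concern.** A false positive or false negative exists only where a yes/no call is compared with a reference truth. The trial's primary measurements are continuous, and it compares two devices in the same patients; no call and no reference is described. As it stands, nobody could take the final data set and state whether the result is promising.

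Two things are at stake. First, the meaning of the rule would have to be settled later, possibly after outcome data have been seen at the 25-patient analysis. Second, the rule is the only stated criterion of success, so the non-inferiority aim has no criterion of its own.

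**Working it through.** **1. Search for the missing definitions.** The two terms occur only in the Statistical Analysis section. Evaluating the rule needs four items: the event that counts as positive, the reference truth, the counting unit (patient, session or visit) and the denominator. None is given, nor is a confidence level for the exact limits. Three FEV1 thresholds of 10% appear elsewhere, and each has another use:

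- a fall over the last 12 months excludes outpatients (Additional Exclusion Criteria);
- a rise by day 9 governs inpatient exclusion and the choice of device on days 10-14 (Additional Exclusion Criteria; Inpatient arm);
- a fall from baseline ends use of the experimental device (Safety Endpoints).

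None is linked to a positive or negative result.

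**2. Whether the gaps could change the verdict.** Assume, purely for illustration, one yes/no call per patient.

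- Part (a), no false positives: with a true rate of 5%, the chance of meeting it is 0.95^n. That is 0.95^10 = 0.60 for 10 calls and 0.95^50 = 0.08 for 50 calls.
- Part (b), rate below 50%: as a point estimate, 24/50 = 48% passes, with exact 95% limits of 33.7% to 62.6%. If the upper limit must be below 50%, at most 17/50 = 34% passes.

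The outcome therefore depends on a denominator and a reading that the plan does not fix. None of these figures says anything about the FEV1 difference between devices.

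**3. Rule against aim.** Aim 1 needs a between-device difference in a continuous change, judged against the largest deficit that would be acceptable. The rule names no measure, no device contrast and no margin. A per-patient responder table with one device as reference could be imagined. It would count disagreements, and would not bound the difference.

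**4. What the ANOVA can and cannot supply.** It can estimate the device contrast, and a confidence interval follows from it. The plan states no significance level, margin or decision rule. To show why a non-significant test is not evidence of non-inferiority:

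- Inputs: n = 40 outpatients (recruitment goal, assuming all complete). Two-sided 5% level and true deficits d in SDs of the paired difference: assumed, because the documents give neither.
- Formula: P(non-significant) = P(|T| < t(0.975, n-1)), where T is noncentral t with n-1 df and noncentrality d√n. For n = 40 the critical value is 2.023 and √40 = 6.325.

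| True deficit d (SD) | d√40 | Non-significant, n = 40 | Non-significant, n = 10 inpatients |
|---|---|---|---|
| 0.1 | 0.632 | 90.5% | 94.1% |
| 0.2 | 1.265 | 76.5% | 91.2% |
| 0.3 | 1.897 | 54.3% | 86.4% |
| 0.5 | 3.162 | 13.1% | 70.7% |

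The 95% CI half-width is t(0.975, n-1)/√n: 2.023/6.325 = 0.32 SD for 40 patients and 2.262/3.162 = 0.72 SD for 10. A period term barely alters these (0.32 and 0.73). With no SD in the documents, none of this converts to FEV1 units.

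**The case against.** Several points on the other side are fair.

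- **The paragraph is about spirometry.** Its first sentence tabulates spirometry by condition and group, so a reader who inferred that the rule has nothing to do with the primary endpoint would go too far. The link is by context only, however, and context does not supply a classification or a reference.
- **The analysis can address the primary endpoint.** It would be tempting to say that no planned output bears on non-inferiority. The documents do not support that: the ANOVA can yield the device contrast. What is missing is the margin and the decision rule.
- **Nothing says that non-significance will be read as non-inferiority.** A reader might infer it from the no-difference hypothesis. It is a foreseeable misreading, not a stated plan. Nor do the documents say that the rule will be applied at 25 patients.
- **The illustration depends on the assumed effect.** At 40 patients it runs from 90.5% down to 13.1%, so no single figure should be cited as the size of the problem.
- **This is a pilot, and no consequence is attached to the word promising.** That excuses limited power and the absence of a definitive test. It does not excuse a stated verdict that cannot be worked out.

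**Conclusion.** The concern holds in this form: the only success criterion cannot be evaluated as written, and defining its terms would make it computable without making it answer aim 1. The defect is qualitative and rests on what the text leaves out, so it depends on none of the illustrative figures. Those assume full completion, a two-sided 5% level and a chosen deficit, and they show only that a non-significant ANOVA cannot stand in for the missing criterion. They do not show that 50 patients is too few; without an SD and a margin that cannot be judged. The point should be fixed before outcome data are analysed, because a criterion chosen afterwards would carry little weight.

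**What to change.** Before any outcome analysis, including the one at 25 patients, delete both false-positive/false-negative sentences and state a criterion on the primary endpoint: the estimate and 95% CI for the within-patient PIAPD minus SACD difference in pre-to-2-hour FEV1 change, from a model that includes period. Judge it against a non-inferiority margin, or a precision target suited to a pilot, that the sponsor states and justifies in advance.

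The same paragraph should settle four things:

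- **Measures:** whether FEV1 alone decides the verdict or pulse oximetry does too, since aim 1 names both.
- **Sessions:** which outpatient sessions enter. On day 1 the timing is explicit ("pulse oximetry will be obtained before and 2 hours after airway clearance"). For the twice-weekly tests the protocol says only that measurements are taken before and after; aim 1 suggests 2 hours, and this should be confirmed. Using day 1 alone would set aside the two weeks of home testing, which matters for an aim about at-home use. A defined average that includes the home sessions is the alternative.
- **Settings:** how the two designs are combined, or that they are reported separately. Outpatients spend two weeks on each device; the inpatient randomised comparison is one session per device on Days 4 and 5.
- **Timing:** that the verdict is made once, at the final analysis.

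The cost is a paragraph of text, the choice and justification of a margin or precision target, and IRB approval of the amendment, which Statement of Compliance requires before it takes effect. No new data are needed.
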